Rash/Erythema	2.5 – 5 cm	5.1 – 10 cm	> 10 cm	Necrosis or exfoliative dermatitis
Pruitis/Itching	No interference with activity	Some interference with activity	Significant; prevents daily activity	ER visit or hospitalization
Fever	38.0 – 38.4 °C 100.4 – 101.1°F	38.5 – 38.9°C 101.2 – 102.0°F	39.0 – 40°C 102.1 – 104 °F	> 40°C > 104 °F
Tachycardia - beats per minute	101 – 115	116 – 130	> 130	ER visit or hospitalization for arrhythmia
Bradycardia -	50 – 54	45 – 49	< 45	ER visit or

beats per minute***				hospitalization for arrhythmia
Hypertension (systolic) - mm Hg	141 – 150	151 – 155	> 155	ER visit or hospitalization for malignant hypertension
Hypertension (diastolic) - mm Hg	91 – 95	96 – 100	> 100	ER visit or hospitalization for malignant hypertension
Hypotension (systolic) – mm Hg	85 – 89	80 – 84	< 80	ER visit or hospitalization for hypotensive shock
Respiratory Rate – breaths per minute	17 – 20	21 – 25	> 25	Intubation
Other illness or clinical adverse event (as defined according to applicable regulations)	No interference with activity	Some interference with activity not requiring medical intervention	Prevents daily activity and requires medical intervention	ER visit or hospitalization

Table 4. Laboratory Adverse Events

Blood Parameter	Reference Range*	Mild/Moderate	Severe/Critical
Sodium – Hyponatremia mmol/L	136-144	126-135	≤125
Sodium – Hypernatremia mmol/L	136-144	145 – 155	≥156
Potassium – Hyperkalemia mmol/L	3.6-5.1	5.2-6.0	>6.0
Potassium – Hypokalemia mmol/L	3.6-5.1	3.0-3.5	<3.0
Glucose – Hypoglycemia mg/dL	65 – 110	45-64	<45
Glucose – Hyperglycemia mg/dL	65 – 110	111-450	>450, or insulin requirement, or hyperosmolar coma
Blood Urea Nitrogen, BUN mg/dL	8-25	26-150	> 150 or requires dialysis
Creatinine – mg/dL	0.4-1.0	1.1-5.8	>5.8 or requires dialysis
Calcium – hypocalcemia mg/dL	8.9-10.3	6.6-8.8	≤6.5
Calcium – hypercalcemia mg/dL	8.9-10.3	10.4-12.9	≥13.0
Albumin – Hypoalbuminemia g/dL	3.5-4.8	<3.5	-----
Total Protein – Hypoproteinemia g/dL	6.1-7.9	<6.1	-----
Alkaline phosphate unit/L	32-91	<91	-----
ALT unit/L	≤ 33	>33	-----
AST unit/L	15-41	>41	-----
Bilirubin mg/dL	0.3-1.2 mg/dL	1.3-20	>20
Cholesterol mg/dL	≤ 199	>199	-----
Hemoglobin (Female) - g/dL	11.4-14.4	6.6-11.3	≤ 6.5
WBC low x 10 ³ /mCL	4-10	2-3.9	< 2.0
WBC high x 10 ³ /mCL	4-10	11-50	>50
Eosinophils x 10 ³ /mCL	<0.36	>0.37	Hyper eosinophilic
Platelets-high x 10 ³ /mCL	150-400	401-999	>999
Platelets-low x 10 ³ /mCL	150-400	51-149	<50

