Urine Parameter	Reference Range	Mild/Moderate	Severe/Critical
Protein	none	trace	Hospitalization or dialysis
Glucose	none	trace	Hospitalization for hyperglycemia
Blood (microscopic) – red blood cells per high-power field (RBC/hpf)	none	trace	gross blood or hospitalization or packed red blood cells (PRBC) transfusion

*Specific to EUH Laboratories

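### Table 4 grades alkaline phosphatase in the wrong direction and gives no class to urine results worse than trace; the effect is limited to the consistency of minor safety listings

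*Combined protocol and SAP*

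**What the plan says.** Section 7.3 states that standard laboratory values at baseline, month 6 and month 12 are graded by Table 4. It adds that withdrawal of study drug is at the discretion of the PI and the Safety Officer, informed by a severity grade of 3 or 4 and by likely relatedness. Table 4 has three columns of limits: reference range, Mild/Moderate and Severe/Critical.

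The alkaline phosphatase row (labelled as phosphate) reads "Alkaline phosphate unit/L 32-91 <91", with no severe class. The next two rows, also liver enzymes, are graded when high: "ALT unit/L ≤ 33 >33" and "AST unit/L 15-41 >41".

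The urine rows go from none to trace to a severe class: "Protein none trace Hospitalization or dialysis" for protein and "Glucose none trace Hospitalization for hyperglycemia" for glucose. Microscopic blood follows the same pattern, ending in gross blood, hospitalization or transfusion.

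The eosinophil row reads "<0.36 >0.37 Hyper eosinophilic" and the platelets-low row "150-400 51-149 <50". WBC high has a reference of 4-10 and then Mild/Moderate 11-50. No other section corrects or supplements these limits.

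**The concern.** A written grading table exists so that the same result gets the same class whoever applies it. The alkaline phosphatase row, applied literally, lists normal values as adverse and leaves elevations unlisted. It cannot be rescued as a rule for low values: albumin and total protein, which are graded when low, are cut at the lower end of their reference ranges, whereas 91 is the upper end of this one. In the urine rows the mildest abnormality is listed, while a worse finding in a participant who is not hospitalized has no place.

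What is at stake is the consistency of the safety listings. The Safety Officer sees semi-annual reports (section 7.5.1), and section 2 includes safety in the primary objective, so these listings should mean the same thing throughout the trial.

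**Working it through.** **Inputs.** Limits from Table 4; grading times from section 7.3; 40 participants from section 3.3. The plan gives no figure of its own to reproduce here. Each row was checked at the precision printed in the table and only in the direction it is meant to grade, so a row that grades only high or only low values is not counted as faulty for that.

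**Alkaline phosphatase.**
- Whole numbers in the reference range 32-91: 91 − 32 + 1 = 60.
- Those also below 91, so both normal and graded: 90 − 32 + 1 = 59.
- The value 91 is normal only. Every value from 92 upward is in no class.
- With Mild/Moderate set to >91, a check of every whole number from 32 to 300 finds no gap and no overlap.

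**Urine.** In all 3 rows, a result above trace that does not meet the severe definition is neither none, nor trace, nor severe.

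**Narrow gaps.**
- Eosinophils: below 0.36, then above 0.37. At two decimals, 0.36 and 0.37 have no class (2 values).
- Platelets-low: 51-149, then below 50. Exactly 50 has no class (1 value). The sodium-low row, "136-144 126-135 ≤125", shows the usual pattern: the lower band is closed with ≤. Calcium-low and hemoglobin do the same.
- WBC high: 4-10, then 11-50. If counts are reported to one decimal, 10.1 to 10.9 have no class (9 values). If they are reported as whole numbers, there is no gap. The WBC-low row, with its limit of 3.9, suggests one decimal, but the WBC-high limits are printed as whole numbers.

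**How much of the table is affected.** There are 23 blood rows.
- Reference and Mild/Moderate bands meet in 20 of 23. The exceptions are alkaline phosphatase, eosinophils and, at one decimal, WBC high.
- Of the 23 rows, 6 have no severe class and 1 (eosinophils) has a non-numeric one, leaving 23 − 7 = 16 with both bands as numbers. The bands meet in 15 of these 16; platelets-low is the exception.

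**Exposure.** 40 participants × 3 grading times = at most 120 panels of each type. Table 1 places the first blood count, chemistry profile and urinalysis at screening, which is taken here as the baseline panel. The documents give no rates of abnormal results, so the number of results affected cannot be computed.

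**The case against.** The strongest reply is that nothing important depends on these cells. Table 4 grades feed none of the endpoints in sections 4.9 and 4.10 and are not named in the analysis of section 4.14. The IRB reporting criteria and SAE definitions in section 7.5.2 do not use the Table 4 limits. Withdrawal needs a grade of 3 or 4, a relatedness judgement and the discretion of two people, and alkaline phosphatase has no severe class whichever way the sign points. Section 7.4.1 has experienced clinicians reviewing the tests. They would probably see a one-character slip beside a printed reference range and place a urine result above trace in Mild/Moderate. All of this stands, and it keeps the impact minor. It does not make the written rule right: the intended reading has to be supplied by the person applying it. The general row for other clinical events in Table 3 does not fill the gap either, because it grades clinical consequences and not the urine value.

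A reader might infer that Table 4 as a whole is unreliable, or that elevated enzymes would go unnoticed and participant protection is weakened. The documents do not support either. The other blood rows meet at the printed precision, and clinical review of the laboratory tests does not depend on the grade. Nor do the narrow gaps carry the same weight as the two main errors: they cover two values, one value, and a range that exists only under one-decimal reporting.

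**Conclusion.** The table is wrong as written in two respects: the direction of the alkaline phosphatase limit, and the missing class for urine results worse than trace. Both lie in a rule that the trial applies, and both are worth correcting. The size is small: consistency of Mild/Moderate listings over at most 120 graded panels, with no effect on the bone density analysis.

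The effect on withdrawal is little or none. Platelets of exactly 50 and urine results above trace sit next to a severe class and could in principle be read into it, but the decision remains discretionary. This assumes that Severe/Critical corresponds to grade 3 or 4, since Table 4 carries no grade numbers.

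The alkaline phosphatase point assumes that the printed sign is the sign in the source. The ALT and AST rows suggest that the opposite sign was intended. A misread of that one character in the PDF text cannot be fully excluded, although the > signs in neighbouring rows are intact.

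**What to change.** Two corrections:
- Alkaline phosphatase, Mild/Moderate: >91, after checking the sign against the source table.
- Urine protein, glucose and microscopic blood, Mild/Moderate: trace or greater, not meeting the Severe/Critical definition.

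In the same edit, as a tidy-up:
- Platelets-low, Severe/Critical: ≤50, with 51-149 unchanged.
- Eosinophils, Mild/Moderate: ≥0.36, not meeting the Severe/Critical definition.
- WBC high, Mild/Moderate: >10 to 50, if counts are reported to one decimal.

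This is at most 1 + 3 + 3 = 7 cells in one table, with no new tests, visits or participants. The downside is that slightly more mild urine, eosinophil and possibly white cell events would be listed. Alkaline phosphatase would be graded only when high, as ALT and AST already are, so values below 32 would have no class.

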7.4. Additional protection against risks

7.4.1 Subject identification and screening for eligibility: Our strict inclusion and exclusion criteria for entry will help to minimize potential risks. All subjects will be monitored closely by frequent clinical assessments and review of safety laboratory tests by experienced clinicians.

7.4.2 Blood sampling: Experienced research nurses will use aseptic techniques for all study blood draws. Participants will be asked to stay hydrated with water the day before the study visit. Universal precautions will be employed in all instances involving human specimens and all blood processed under at least BSL2 conditions. Discomforts associated with venipuncture are rapidly reversible.

7.4.3 DXA: DXA will be performed by experienced technicians who are trained in radiation exposure minimization in patients.

7.4.4 Privacy and confidentiality: The subjects' extracted medical records and data from the study will be initially stored on paper prior to transfer to electronic format. The encrypted electronic record will remain on the principal investigator's password protected computer in his locked office. Confidentiality will be assured by the use of subject codes rather than personal identifiers. The master list connecting the subject codes to identifying information will be secured in the PI's computerized database. All paper subject records will be kept in locked file cabinets in the PI's research office and will be accessible only to the PI and the investigative team. Only institutional review board (IRB)-approved study personnel will have access to individually identifiable information about human subjects. This may include the study PI, co-investigators, research coordinators, and other approved study personnel. All information and materials will be obtained for research purposes only and the data will be kept in strict confidence for use in this proposed research only.

7.4.5 Other: Since the proposed tests are not inherently hazardous, hazard is likely to occur only as the result of impaired participant confidence or sudden unwillingness to complete a test. To avoid this possibility, study personnel will thoroughly explain all tests to potential participants prior to them signing the consent form. Potential participants will have the opportunity to see all test equipment and facilities before giving consent or undergoing testing. Trained personnel will be available at all times to monitor participants' physical and emotional distress. Every effort will be taken to prevent injury or distress that may result from this study. A study physician will be on call for support. A qualified physician will have primary responsibility for outpatient care.

7.5. Data and Safety Monitoring and Reporting: Trained study personnel will be with a participant at all times to monitor patient safety. Adverse events are expected to be uncommon and not pose more than minimal risk to the study participants. The Principal investigator (PI) will review all data collection forms at least semi-annually for completeness and accuracy of the data as well as protocol compliance. The PI will review this protocol on a continuing basis for subject safety and include the results of the review in annual progress reports submitted to the IRB.

7.5.1 Data Safety Officer: A senior faculty Data Safety Officer, [name], MD, FASGE, Associate Professor of Medicine in the Emory University Division of Digestive Diseases, Clinical Director of Gastroenterology at the Emory Clinic, and Director of Gastrointestinal Motility has been designated for this study. [name] is an experienced physician-scientist with expertise in randomized controlled clinical trials and translational science. She will review semi-annual reports created by the Principal Investigator (PI) Dr.

[name] and the Data Coordinating Committee, directed by [name], MS, and make recommendations regarding the continuation of study.

7.5.2 Participant Safety Data Examination, Monitoring Procedures/Oversight: Participant monitoring will be performed by the PI, Co-Investigators, and members of the study team. The IRB Reportable Events Guidelines will be followed. The standard Emory IRB reporting guidelines for AE and SAE reporting will also be followed. Any adverse events will be reported to the IRB within 10 days of the event if it is (a) an unanticipated problem involving risk to participants or others, (b) a death that is possibly, probably, or definitely related to the research, (c) an anticipated event occurring with a greater frequency, duration, or severity than what is described in the protocol related documents, or (d) any other information that suggests the research places participants or others at greater risk of harm than was previously known. A reportable events log will be maintained by the PI and reported annually to the IRB (or more frequently if required.)

All adverse events will be graded as to their attribution (unrelated to protocol, or possibly, probably, or definitely related to protocol). Any AE that is reported to either the PI or the study team by a study subject or by medical staff caring for the subject and which meets the criteria will be documented as such. Adverse events will also be further labeled as “expected” AEs (which are predefined and listed as potential risks in the informed consent), “unanticipated” AEs, and serious adverse events. Serious adverse events (SAE) are predefined as: any experience that suggests a significant hazard, such as events which: a) are fatal, b) are life threatening, c) result in permanent disability, d) require inpatient hospitalization, or e) involve cancer, a congenital anomaly, or drug overdose.

7.5.3 Performance Standards: The Data Coordinating Center (DCC) has worked closely with the clinical team during protocol development to specify performance standards that should be met to achieve high quality of trial conduct. These standards will address screening and recruitment plans and rates, retention plans and rates, missing data, definition of dropout, the intention-to-treat principle (both as a design and analysis issue), completeness of data, procedural adherence, quality control plus plans to address problems that may arise among these interrelated issues. The proposed trial affords investigators an opportunity to revise and standardize the recruitment and retention plans that will be helpful for future trials and cohorts.

7.5.4 Recruitment, Retention and an Intent-To-Treat Design: The clinical investigators and the DCC will work together to establish successful strategies for patient recruitment and patient retention. Screening and recruitment reports will be generated monthly that include actual and expected recruitment statistics. Strategies to address potential problems with recruitment include every two-week telephone calls to each subject to address treatment/intervention adherence, medical record review of previous compliance with study visits, and patient education during the informed consent process about the scientific relevance of their data even if they discontinue the intervention, and the deleterious effect that missing data has on study integrity and credibility. Wording to this effect has been successfully added to informed consent forms to enable patients to make more informed decisions about their willingness to join a trial and to participate in continued follow-up without feeling inappropriately pressured to do so ³⁹.

Plans to minimize missed visits/assessments and minimize dropout will be an important focus during study design. Randomization alone is not sufficient to provide unbiased comparisons of interventions, but one sufficient condition to provide an unbiased comparison is to obtain complete data on all randomized participants. Therefore retention of the cohort is key to ensuring an intention-to-treat design and intention-to-treat analysis (full compliance with treatment/intervention, no missing data and complete follow-up of all participants). Only intent-to-treat analyses fully preserve the validity of assumptions between intervention groups established by randomization.

Valid reasons a patient can be off study include withdrawal of consent at any time during the study or the achievement of all required efficacy and safety end point information. Withdrawal of consent will be used only when the patient no longer wishes to participate in the trial and no longer authorizes the investigators to make efforts to continue to obtain their outcome data. Valid reasons for non-adherence to treatment include an inability to tolerate the intervention, toxicity, physician choice or need for other therapies. All patients will continue to be followed with all scheduled outcome evaluations until the end of the study. This strategy will

allow a true all-inclusive, intent-to-treat design and analysis. Patients will not be labeled 'dropouts' but as 'temporarily inactive' and the patient will be welcomed back to the trial when possible. The designation of 'lost-to-follow-up' will be applied at the end of the trial to patients that remained inactive. Monthly reports will summarize recruitment and retention rates, treatment adherence rates, observed and expected data on attendance to routine clinical visits and the degree of completeness of data capture. The DCC will establish performance standards before the trial. These standards will be reviewed and revised as needed during the trial to enhance the quality of trial conduct.

7.5.5 Data Management Considerations: The DCC will establish processes and work-flow to create and maintain a high quality research database for the trial while preserving the confidentiality of all subjects' data. It is difficult to implement a statistical analysis plan unless a data management plan has been followed to assure data quality and procedural adherence. Quality control will be applied to each phase of data handling to ensure that all data are reliable and have been processed correctly.

7.5.5.1 Case Report Forms (CRFs): The clinical investigators and the DCC will collaborate on the design of CRFs for each study. All CRFs will be designed using Adobe InDesign. Forms questions and lay-out will be optimized for ease of forms completion and ease of data entry.

7.5.5.2 Design of the Data Management System: CRF data as defined and dictated by protocol will be collected and managed using iDataFax or web-based tools (DF Web). iDataFax is a commercially available electronic data capture (EDC) system used to enter, review and modify patient data, and to submit it over the internet to a DataFax server maintained at the Rollins School of Public Health at Emory University. iDataFax provides secure 128 bit SSL encryption of all data and document transmissions over the internet. DataFax is fully 21 CFR Part 11 compliant and its use has been fully validated to FDA standards. The DCC has used iDataFax since 1998 for several NIH funded multicenter clinical trials and multicenter cohort studies. The EDC system has extensive data management features including a data query system to help ensure study credibility. Beyond EDC, DataFax allows data worksheets, source documents, and other participant records to be scanned and securely attached to any data record.

Data queries are reduced through the use of DataFax's powerful edit check features. Extensive data checks, both within and across forms, will be built into the computerized data capture system developed for the trial. Data are checked by comparing values of a field to predefined specifications (for example, minimum and maximum values or specific codes) and by programs written in an internal C-like language that allow for intricate comparisons among multiple fields on the same or on different CRFs. System generated queries requesting correction or clarification of values can be responded to on-line or by faxing/ emailing a corrected version of the CRF. The system provides a mechanism for defining the prescribed patient visit schedule so that queries indicating overdue CRFs are automatically generated. DataFax has a module for exporting CRF data by creating Statistical Analysis System (SAS) datasets. Department of Biostatistics personnel have developed S-Plus functions that produce the code for making tables and graphs in LaTeX, a mark-up language commonly used in mathematical fields for document processing. This set of tools are used by the DCC for generating automated DSMB reports.

7.5.5.3 Data Acquisition Plans and Reports: Data entry will be distributed and the study database will be centralized. For the proposed studies, personnel at the clinical center will enter patient data from the screening, baseline, and follow-up visits into eCRFs on the server at the DCC via the internet. The iDataFax system will generate regular reports (overall and by clinical center) that summarize and track routine data collection. These reports will help the investigative team monitor and maintain data completeness during follow-up and achieve high data capture performance standards by minimizing missed clinical visits, preventing missing data and maintaining high cohort retention rates. Monthly reports will be generated for clinical sites on the status of patient screening and enrollment and on the status of data queries issued by the DCC. These reports will be available to appropriate study personnel on a website developed and maintained by the DCC.

7.5.5.4 Study Material Access: The DCC will maintain a web dashboard. The investigators will access study-related documents through this dashboard including CRFs, the Protocol, meeting minutes, monthly data reports, enrollment and recruitment curves, presentations and publications.

